An analysis of covariance (ANCOVA) model with strata (pooled country, type of basal insulin, baseline HbA1c strata [$\leq 7.5\%$, $>7.5\%$], and prandial insulin dosing plan during the study), and treatment as fixed effects and baseline as a covariate will be used to analyze the 1-hour and 2-hour PPG excursions. However, if the percentage of the patients with missing MMTT data at baseline is higher than 15%, a constrained longitudinal data analysis model (Liu et al. 2009; Lu 2010) will be used instead. Analyses details will be documented in the statistical analysis plan (SAP).

Hypoglycemia rates will be summarized for periods of 30 days, 1 year, and 100 years (severe hypoglycemia only). The rate of severe hypoglycemia per 100 years will be compared between treatment groups using the empirical method. For each of the other categories of hypoglycemia, the number of hypoglycemia events during a specific period (rate) after randomization (for example, 0-12 weeks of treatment period) will be analyzed by using a negative binomial regression model. The model will include treatment and the baseline hypoglycemia rate (measured during lead-in) as a covariate. An offset defined as the log transformation of treatment exposure in the specific period (days)/365.25 days (or 30 days) will be included in the model to estimate the rate of hypoglycemia per year (or per 30 days). The proportion of patients with at least 1 hypoglycemic event in each category (incidence) during a specific period after randomization will be analyzed using a logistic regression model including treatment and baseline hypoglycemia rate value in the model.

Continuous safety variables, as well as the change from baseline for these variables, will be analyzed by MMRM or ANCOVA models. For categorical variables, Fisher's exact test or Pearson's chi-square test will be used to compare treatment groups unless otherwise specified.

Change from baseline to last-observation-carried forward endpoints for the CCI

ITSQ, and CCI will be analyzed using ANCOVA models.

References:

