9.1.4.1. Electronic Clinical Outcomes Assessment

The eCOA diary will wirelessly receive all glucose data directly from the BG meters, thereby increasing the validity of measures reported by the patient and minimizing transcription errors in recording the measures. The use of e-diaries should also allow more complete and accurate capturing of hypoglycemia events, as well as more frequent and timely interactions between investigator and patients as the intensity of their individual diabetes management increases.

The system will be used to collect time of the meal and prandial insulin doses (date, time, and actual dose taken) and the basal insulin dose, 3 days prior to study visits, on the days of 10-point SMBG profiles and at other times as clinically indicated. For patients who are carbohydrate counting, the grams of carbohydrate will be entered for each meal during the 10-point SMBG profile days. Hypoglycemic events will be captured throughout the clinical study in eCOA along with date and time of the BG level if measured and hypoglycemia treatment and outcome data. Additionally, the eCOA system will incorporate study-specific reminders for patients to perform the 10-point SMBG profiles.

Physicians and designated clinical staff will have access via eCOA portal (secure web-based site), to the ongoing near real-time updating of the BG readings, insulin doses administered, hypoglycemic events, and dosing time relative to the meal. Manual inspection of data will support at least weekly patient monitoring as an enhancement to standard of care for patient safety, as well as the potential for reaching an optimum efficacy outcome. Investigative staff will assess clinical data via the eCOA portal and recommend adjustments in basal and prandial insulin (also refer to Section 7.2.1).

An instruction manual will be provided to patients and investigative sites. Additional instruction and training will be provided to the investigative sites regarding data collection, review, retention and archival processes. In the event of eCOA e-diary malfunction or loss, the patient will be instructed to immediately contact the investigative site for instructions regarding replacement of the equipment.

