Study Procedures	Lab/Imaging Criteria	Missing HbA1c at baseline/at the primary endpoint	Mixed (monitoring and clinical database)	Central laboratory data to indicate that a). HbA1c is not collected at both Visit 7 and Visit 8 or b). HbA1c is not collected at the primary endpoint (only applicable to patients who completed the primary endpoint without early discontinuation from the study).
Study Procedures	Visit Schedule Criteria		Programmable (clinical database)	CRF Subject Visit panel data to indicate that 2 consecutive office visits are completely missing.
Study Procedures	Other	Electronic Clinical Outcomes Assessment (eCOA)	Programmable (clinical database)	Comparison of patient data from CRF and eCOA to identify randomized patients who have no ed diary data entered.
Administrative/Oversight	Suspected Misconduct		Non Programmable (monitoring)	Site staff sharing account details for systems (e IWRS, EDC or ePresentOnline). Suspected falsification of data.
Safety	Safety Mailings		Non Programmable (monitoring)	Lack of, significant delay in safety mailing review (significant delay defined as a delay of 90 days).
Safety	SAEs		Non Programmable (monitoring)	Failure to report an SAE within 24 hours of the investigator being made aware of the SAE. Failure to respond to SAE queries.

Description of Important Protocol Deviations

Category	Sub-categories	Description	Source	Methods of Identification
Safety	Other	Failure to report product complaint within 24 hours.	Non Programmable (monitoring)	Identified by CRA as captured in sCTMS.

Abbreviations: # = number of inclusion/exclusion criteria in protocols; CGM = continuous glucose monitoring; CRA = clinical research associate; CRF = clinical (case) report form; CRP = clinical research physician; CRS = clinical research scientist; CT = clinical trial; HbA1c = hemoglobin A1c; ICD = informed consent document; eCOA = Electronic Clinical Outcome Assessments; EDC = Electronic Data Capture; IWRS = interactive Web Response System; MedDRA = Medical Dictionary for Regulatory Activities; SAE = serious adverse event; sCTMS = Simplicity Clinical Trial Management System; T1D = type 1 diabetes; yrs = years.

Furthermore, of the above listed important protocol deviations, the following may significantly impact the results of the primary objective:

- lack of informed consent
- have any hematological condition that may interfere with HbA1c measurement
- missing HbA1c at both Visit 7 and Visit 8, or missing HbA1c at the primary endpoint.

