6.12.4.1. Hypoglycemic Events

Hypoglycemia events that occur during the study outside the MMTT will be captured using an eCOA diary starting from Visit 2 through Visit 801. Whenever hypoglycemia is suspected, the patient should record the blood glucose value, any associated symptoms, and the treatment administered in eCOA. A set of events is counted as 1 event in analysis if it consists of an originating event and subsequent continuing events as marked by the patient in eCOA, or the duration between adjacent events is ≤ 30 minutes. The event with the highest severity will be selected for analysis with severity determined in the order of: 1) it is a severe hypoglycemia, 2) it has symptoms of hypoglycemia reported, and 3) it has the lowest blood glucose value. If there are multiple events tied in all 3 aspects, the event with the largest number of non-missing responses to the questions of nocturnal hypoglycemia and postmeal time frame will be selected. If there are still multiple events tied, the latest event (based on data entry time) will be selected.

The following types of hypoglycemia events will be derived in the analysis data sets: documented hypoglycemia, severe hypoglycemia, nocturnal hypoglycemia (documented and occurring between bedtime and waking), probable symptomatic hypoglycemia, and overall hypoglycemia. Only severe hypoglycemia will be collected as AEs and all episodes of severe hypoglycemia will be considered as SAEs. Documented hypoglycemia (including documented symptomatic hypoglycemia, documented asymptomatic hypoglycemia and documented unspecified hypoglycemia) will be based on blood glucose (BG) ≤ 70 mg/dL. In addition, documented clinically significant hypoglycemia with similar criterion as above documented hypoglycemia except for the threshold of BG < 54 mg/dL will be summarized. Hypoglycemia identified by CGM for patients in the CGM Addendum will not be included in these analyses.

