[Table 6.6](#) provides detailed statistical methods for each endpoint related to hypoglycemia. For these analyses, hypoglycemia events prior to discontinuation of IP will be summarized. For the analysis period prior to Week 26, the analysis data will include data from all 3 treatment groups. For the analysis period after Week 26, the analysis data will only include data from the 2 double-blind treatment groups. Additional analyses for other types of hypoglycemic events not mentioned in the table and for the post-treatment period may be conducted as needed.

The incidence and number of episodes of hypoglycemia (regardless of the type of hypoglycemia event) during the MMTT will be summarized by treatment and time relative to the meal (≤ 0.5 , ≤ 1 , ≤ 2 , ≤ 4 , >1 to ≤ 2 and >2 to ≤ 4 hours after start of the meal) and analyzed by Fisher's exact test.

A listing of patients with at least 1 severe hypoglycemia reported (as SAE) after randomization will be provided.

A list of MedDRA PTs will be used for the narrow search of potential severe hypoglycemia in spontaneously reported AEs. The events identified through the search strategy that are also

reported as SAEs will be summarized and compared between treatments. Fisher's exact test will be used to assess the treatment difference in the proportion of patients with potential severe hypoglycemia.

Table 6.6. Summary of Analyses for Endpoints Related to Hypoglycemia

Endpoint	Analysis Period	Statistical Method
Rate of hypoglycemic events (per patient per 30 days / year) All Documented ^a Nocturnal ^a Documented Symptomatic ^a Overall Non-Nocturnal (or Daytime) (Documented and between waking and bedtime) ^a Probable Symptomatic	0-4, 0-12, 0-26, 4-8, 8-12, 12-26, 26-52, 0-52 weeks	Negative binomial regression with treatment, and baseline hypoglycemia event rate with the same category of the dependent variable as covariates, log (exposure/30/365.25 days) as the offset in the model.
Incidence of hypoglycemic events All Documented ^a Nocturnal ^a Documented Symptomatic ^a Overall Non-Nocturnal (or Daytime) (Documented and between waking and bedtime) ^a Probable Symptomatic	0-4, 0-12, 0-26, 4-8, 8-12, 12-26, 26-52, 0-52 weeks	Logistic regression with treatment, baseline hypoglycemia event rate with the same category of the dependent variable as covariates.

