Rate of postmeal hypoglycemic events (per patient per 30 days / year) for all 3 main meals Documented Symptomatic ^a Documented Asymptomatic ^a	≤ 0.5 , ≤ 1 , ≤ 2 , ≤ 4 , >1 to ≤ 2 and >2 to ≤ 4 hours after start of a meal within 0-12, 12-26, 0-26, 26-52, 0-52 weeks	Negative binomial regression with treatment, baseline postmeal hypoglycemia event rate with the same category of the dependent variable as covariates, log (exposure/30/365.25 days) as the offset in the model.
Incidence of postmeal hypoglycemic events for all 3 main meals Documented Symptomatic ^a Documented Asymptomatic ^a	≤ 0.5 , ≤ 1 , ≤ 2 , ≤ 4 , >1 to ≤ 2 and >2 to ≤ 4 hours after start of a meal within 0-12, 12-26, 0-26, 26-52, 0-52 weeks	Logistic regression with treatment, baseline postmeal hypoglycemia event rate with the same category of the dependent variable as covariates.
Rate of severe hypoglycemic events (per patient per year / 100 years)	0-12, 0-26, 12-26, 26-52, 0-52 weeks	Exposure adjusted rate per year / 100 years (calculated by total number of events divided by total exposure for individual patients) will be provided and the empirical method (see Appendix 1 for details) will be used for treatment comparison.

Summary of Analyses for Endpoints Related to Hypoglycemia

Endpoint	Analysis Period	Statistical Method
Incidence of severe hypoglycemic events	0-12, 0-26, 12-26, 26-52, 0-52 weeks	Proportion of patients with severe hypoglycemia will be reported. The treatment comparison will be based on a logistic regression model with treatment and baseline rate as a covariate.
Rate of postmeal severe hypoglycemic events (per patient per year / 100 years) for all 3 main meals	0-12, 12-26, 0-26, 26-52, 0-52 weeks	Due to limit data for the rare event, only summary statistics will be provided by treatment. No statistical comparison will be conducted.
Incidence of postmeal severe hypoglycemic events for all 3 main meals	0-12, 12-26, 0-26, 26-52, 0-52 weeks	Fisher exact test will be used for treatment comparison.

^a All documented hypoglycemia and the subcategories based on the thresholds of blood glucose ≤ 70 mg/dL and blood glucose < 54 mg/dL will be analyzed, except for postmeal hypoglycemia for which only the threshold of ≤ 70 mg/dL will be applied.

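### Non-severe hypoglycemia comes only from the e-diary, but no rule stops patients with no e-diary data in a window from being analyzed as event-free

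*Protocol*

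**What the plan says.** **Source of events.** SAP 6.12.4.1 states: "Hypoglycemia events that occur during the study outside the MMTT will be captured using an eCOA diary starting from Visit 2 through Visit 801". Protocol 9.4.1 agrees. Severe events have a second source: "Only severe hypoglycemia will be collected as AEs and all episodes of severe hypoglycemia will be considered as SAEs".

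**Denominator.** The Protocol (Synopsis, repeated in 10.3.4) sets the offset for every non-severe category: "An offset defined as the log transformation of treatment exposure in the specific period (days)/365.25 days (or 30 days". SAP Table 6.6 repeats it as "log (exposure/30/365.25 days) as the offset in the model". Incidence is a logistic regression on having at least one event and has no exposure term. Both models carry the lead-in hypoglycemia rate as a covariate (SAP 6.2 and Table 6.6).

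**Analysis set.** In SAP Table 6.2 the 26-week hypoglycemia row names the Safety Population and nothing more; the 52-week row names its double-blind part. In the same table, the 26-week rows for 10-point SMBG, 1,5-AG, the ITSQ and safety laboratory tests require a baseline and a postbaseline observation.

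**Foreseen gaps.** SAP Table 6.3 plans a programmed comparison "to identify randomized patients who have no ed diary data entered" (read as e-diary) and treats a hit as an important protocol deviation. That deviation is not among those in SAP 6.9 that exclude a patient from the Per Protocol population. Protocol 9.1.4.1 covers device failure operationally: "In the event of eCOA e-diary malfunction or loss, the patient will be instructed to immediately contact the investigative site". Neither document says how such patients or periods enter the hypoglycemia models.

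**The concern.** The numerator is observed only while the diary is working; the denominator runs for as long as the patient is on investigational product. A patient on treatment who contributes no eCOA data to the Week 0 to 26 window can add up to 26 weeks of exposure with zero events to the rate model, and a no-event outcome to the incidence model. These are false zeros caused by data capture. They are separate from time after stopping treatment, which the plan already excludes.

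The rate and incidence of documented symptomatic hypoglycemia, overall and postmeal, are the endpoints of Objectives 9 and 10. At stake are the absolute figures that will be reported and the between-arm comparisons, in particular the incidence odds ratio, which has no offset to absorb anything.

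**Working it through.** The documents give no hypoglycemia rate, dispersion or diary-completion figure, so there is no planned value to reproduce. Every gap size below is an assumption.

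**1. Who enters as event-free.**
- Lead-in data present, no eCOA data in the window: the baseline covariate exists, exposure is positive and the event count is zero. The patient stays in both models.
- No eCOA data at any time: the lead-in rate is unobserved too. Set to zero, the patient stays in as event-free; treated as missing, the patient drops out of both models. The SAP does not say which.

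**2. Absolute rate.** Let u be the share of an arm's exposure that comes from patients with no data. Observed rate = true rate × (1 − u), so each 1% uncovered lowers the rate by 1%.

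**3. Rate ratio.** Observed ratio = true ratio × (1 − u_trt)/(1 − u_ctl).
- Equal gaps: factor 1.00.
- 5% versus 2% (treatment versus control): 0.95/0.98 = 0.97.

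A negative binomial simulation (436 per arm, half a year, assumed 36 events per patient-year, assumed dispersion 1, true ratio 1.00, 150 runs per scenario) agrees. It assumed that events in uncovered time are lost. With equal gaps (3% of patients with no data and 10% of days missing in both arms), the exposure offset gave a ratio of 1.01 and a control rate of 31.1 against a true 36. The standard error of the log ratio was 0.074, against 0.071 when observed time was used.

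**4. Incidence.** Let p be true incidence and m the share of patients with no data. Observed incidence = p(1 − m).

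No true difference, m = 3% in the treatment arm and 1% in control:

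| p | Observed, treatment | Observed, control | Odds ratio |
|---|---|---|---|
| 80% | 77.6% | 79.2% | 0.91 |
| 90% | 87.3% | 89.1% | 0.84 |
| 95% | 92.15% | 94.05% | 0.74 |

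For the last row the odds are 0.9215/0.0785 = 11.74 and 0.9405/0.0595 = 15.81, and 11.74/15.81 = 0.74. On planned arm sizes, 3% of the 327 open-label patients is about 10 and 1% of 436 is about 4.

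True difference of 95% versus 90% (odds ratio 2.11), equal m in both arms:
- m = 2%: 93.1% versus 88.2%, odds ratio 1.81.
- m = 5%: 90.25% versus 85.5%, odds ratio 1.57.

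Equal gaps therefore cancel in the rate ratio but not in the odds ratio.

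**5. Would replacing the offset by covered days be safe?** Suppose 36 events per year, routine readings on 90% of days, and every symptomatic event tested and recorded. The chance of at least one event on a day is 1 − exp(−36/365.25) = 0.094. An event creates its own record, so covered days are 0.9 + 0.1 × 0.094 = 0.909 of all days, and the rate is overstated by 1/0.909 − 1 = 10%. The exposure offset is correct in this setting. With routine readings at 90% versus 95% of days and no treatment effect, covered days give 0.955/0.909 = 1.05.

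**The case against.** **The diary is event-driven.** Patients are asked to record when they suspect hypoglycemia, so a day with no entry may be truly event-free. A reader might infer that every unrecorded day is missing and that the offset should become covered days. The documents do not support that, and step 5 shows that such an offset depends on the outcome. Nor does every non-severe event need a reading: probable symptomatic hypoglycemia is defined without one. This stands against a day-level remedy. It does not explain a whole window with no data. The shortest window in Table 6.6 is 4 weeks, and Protocol 9.1.4.2 asks for at least 4 readings a day, about 28 × 4 = 112 readings.

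**Patients with no diary data may drop out anyway** through the baseline-rate covariate. This is possible, but it rests on an unwritten rule and does not help for patients who have lead-in data.

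**Rate ratios.** A reader might infer that diary gaps bias them generally. They do so only when coverage differs by arm. Different diary behavior in the open-label postmeal arm is plausible but nowhere documented; diary and 10-point profile requirements are the same in all arms through Week 26. Even the 0.97 above is a log shift of 0.031, under half of a standard error of about 0.07.

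**Safeguards.** Meter data transfer wirelessly, sites can inspect them at least weekly, hypoglycemia data are reviewed at visits, and the no-diary deviation is summarized by arm. These should keep the number small and make an imbalance in wholly uncovered patients visible. They do not say how such patients are analyzed.

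**Severe hypoglycemia.** A reader might extend the point to it. It is also reported as an SAE, and its rate, "calculated by total number of events divided by total exposure for individual patients", properly stays on full exposure.

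**Conclusion.** The point holds at patient level for the non-severe categories. Applied as written, the plan counts a patient with lead-in data but no eCOA data in the window as event-free, and it leaves open what happens to a patient with no eCOA data at all. Absolute rates and incidence are biased down in proportion to the gap. The incidence odds ratio is pulled toward 1 under equal gaps and shifted under unequal ones. The rate ratio moves only with unequal coverage.

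The size cannot be stated from the documents. The rate ratio of 0.97 assumes gaps of 5% versus 2%; the odds ratios of 0.74 to 0.91 assume gaps of 3% versus 1% and incidences of 95% down to 80%. Effects on standard errors look minor under the assumed settings. Objectives 9 and 10 sit outside the multiplicity-controlled family, and the primary HbA1c analysis and the sample size are untouched. The change is still worth making before analysis, because it removes clear false zeros.

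**What to change.** In SAP 6.12.4.1 and Tables 6.2 and 6.6, for the non-severe categories only:

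1. Exclude from the rate and incidence models any patient with no eCOA data in the analysis window, meaning no transmitted meter reading and no diary entry.
2. Treat the baseline rate as missing, not zero, when there are no lead-in eCOA data.
3. Report eCOA coverage by arm.
4. Keep treatment exposure as the primary offset for all other patients. Use eCOA-covered days only in a sensitivity analysis, for the reason in step 5.
5. Leave severe hypoglycemia on full exposure.

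The cost is a few lines of SAP text and a window-level extension of the check that Table 6.3 already programs. The models lose a few patients and the reported rates rise slightly. The exclusion also assumes that patients with no data resemble those who remain, which the coverage table helps the reader to judge.

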3.1. Study Rationale

Prandial insulin with faster-onset and/or faster-offset characteristics might reduce glycemic excursions and decrease the incidence of delayed postprandial hypoglycemia compared to currently available rapid-acting insulin analogs. The insulin analog, insulin lispro (Humalog®), has been shown to be absorbed more quickly than regular human insulin (Humalog package insert, 2015). In healthy volunteers given subcutaneous (SC) doses of insulin lispro ranging from 0.1 to 0.4 U/kg, peak serum levels were seen 30 to 90 minutes after dosing. Rapid-acting insulins have been shown to have a more rapid onset of action compared to human insulin; however, the general consensus is that they are not rapid enough to match carbohydrate absorption and many patients are unable to achieve optimal glycemic control. An ultra-rapid-acting prandial insulin with pharmacokinetic (PK) and glucodynamic (GD) profiles that demonstrate faster absorption and onset of action may better match carbohydrate absorption and lead to improved postprandial control. The time action profile of rapid-acting insulin could be enhanced through the addition of excipients to an existing formulation to increase capillary blood flow and/or enhance vascular permeability. An ultra-rapid insulin (URI) would be useful in the treatment of type 1 diabetes (T1D) and type 2 diabetes (T2D) when delivered by multiple daily injections (MDI), by continuous SC insulin infusion (CSII), and in the development of closed loop insulin delivery systems.

The aim of this study is to demonstrate that an ultra-rapid formulation of insulin lispro, LY900014, is noninferior to insulin lispro on glycemic control as measured by change from baseline to Week 26 in hemoglobin A1c (HbA1c) in patients with T1D, when administered in a double-blind manner as prandial insulin in combination with basal insulin glargine or insulin degludec.

